#### **7.4.4 Criteria to Resume Treatment (BMS-986205 and Nivolumab)**

Participants may resume treatment with study treatments when the drug-related AE(s) resolve to Grade  $\leq$  1 or baseline value, with the following exceptions:

- Participants may resume treatment in the presence of Grade 2 fatigue.
- Participants who have not experienced a Grade 3 drug-related skin AE may resume treatment in the presence of Grade 2 skin toxicity.
- For participants with Grade 2 AST, ALT and/or Total Bilirubin abnormalities, dosing may resume when laboratory values return to baseline and management with corticosteroids, if needed, is complete.
- Participants with combined AST/ALT AND total bilirubin values meeting discontinuation parameters ([Section 8.1.1](#)) should have treatment permanently discontinued.
- Drug-related pulmonary toxicity, diarrhea or colitis must have resolved to baseline before treatment is resumed. Participants with persistent Grade 1 pneumonitis after completion of a steroid taper over at least 1 month may be eligible for retreatment if discussed with and approved by BMS Medical Monitor/designee.

Participants with drug-related endocrinopathies adequately controlled with only physiologic hormone replacement may resume treatment after consultation with the BMS Medical Monitor/designee. Adrenal insufficiency requires discontinuation regardless of control with hormone replacement.

For participants who have BMS-986205 held for elevations of methemoglobin, dosing may resume when the methemoglobin levels have decreased to below the institutional ULN and any associated AEs have resolved to Grade  $\leq$  1 or baseline value. Dose modification of BMS-986205 should be considered when resuming after a delay (see [Section 7.4.2](#)).

[REDACTED]

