## **8 DISCONTINUATION CRITERIA**

### **8.1 Discontinuation from Study Treatment**

Participants **MUST** discontinue investigational product (and non-investigational product at the discretion of the investigator) for any of the following reasons:

- Participant's request to stop study treatment. Withdrawal of consent/assent may be requested by participants, parents, guardians, or legally acceptable representatives, in accordance with

local regulations. The wishes of minor participants to withdraw their assent should also be respected. Participants who request to discontinue study treatment will remain in the study and must continue to be followed for protocol specified follow-up procedures. The only exception to this is when a participant specifically withdraws consent for any further contact with him/her or persons previously authorized by the participant to provide this information.

- Any clinical AE, laboratory abnormality or intercurrent illness which, in the opinion of the investigator, indicates that continued participation in the study is not in the best interest of the participant
- Termination of the study by BMS
- Loss of ability to freely provide consent through imprisonment or involuntarily incarceration for treatment of either a psychiatric or physical (eg, infectious disease) illness
- Additional protocol-specified reasons for discontinuation ([Section 8.1.1](#))
- Documented investigator-assessed progression as defined by RECIST v1.1 (see [Appendix 12](#)) unless participant meets criteria for treatment beyond progression

In the case of pregnancy, the investigator must immediately notify the Sponsor or designee of this event. In most cases, the study treatment will be permanently discontinued in an appropriate manner (eg, dose tapering if necessary for participant safety). Please contact the Sponsor or designee within 24 hours of awareness of the pregnancy. If the investigator determines a possible favorable benefit/risk ratio that warrants continuation of study treatment, a discussion between the investigator and the Sponsor or designee must occur.

Refer to the Schedule of Activities for data to be collected at the time of treatment discontinuation and follow-up and for any further evaluations that can be completed.

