### **8.1.1 BMS-986205 and Nivolumab Dose Discontinuation**

BMS-986205 and nivolumab treatment should be permanently discontinued for the following:

- Any occurrence of serotonin syndrome
- Any Grade 2 drug-related uveitis, eye pain or blurred vision that does not respond to topical therapy and does not improve to Grade 1 severity within the time frame permitted for dose delays OR requires systemic treatment
- Any event requiring more than 1 dose reduction of BMS-986205 (see [Section 7.4.2](#)), except for those related to methemoglobinemia or QTc prolongations, which require only discontinuation of BMS-986205 alone; subjects may continue to receive nivolumab in these situations (see also [Section 8.1.2](#))
- Any drug-related event requiring 10 mg per day or greater prednisone or equivalent for more than 12 weeks, except for adrenal replacement steroid dose >10mg.
- Immune-mediated encephalitis of any grade
- Any Grade 3 non-skin, drug-related AE lasting > 7 days, or recurs with the following exceptions for laboratory abnormalities, diarrhea, colitis, neurologic toxicity, drug-related uveitis, pneumonitis, bronchospasm, hypersensitivity reactions, infusion reactions, and endocrinopathies:
  - Grade 3 drug-related diarrhea, colitis, neurologic toxicity, uveitis, pneumonitis, bronchospasm, myocarditis, hypersensitivity reaction, or infusion reaction of any duration requires discontinuation
  - Grade 3 drug-related endocrinopathies, adequately controlled with only physiologic hormone replacement do not require discontinuation. Adrenal insufficiency requires discontinuation regardless of control with hormone replacement.
  - Grade 3 drug-related laboratory abnormalities do not require treatment discontinuation except:
    - ◆ Grade 3 drug-related thrombocytopenia > 7 days or associated with bleeding requires discontinuation
    - ◆ Any drug-related liver function test (LFT) abnormality that meets the following criteria require discontinuation:
      - Grade  $\geq 3$  drug-related AST, ALT or Total Bilirubin requires discontinuation\*
      - Concurrent AST or ALT > 3 x ULN and total bilirubin > 2x ULN
- \* In most cases of Grade 3 AST or ALT elevation, study treatment(s) will be permanently discontinued. If the investigator determines a possible favorable benefit/risk ratio that warrants continuation of study treatment(s), a discussion between the investigator and the BMS Medical Monitor/designee must occur.

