- Any Grade 4 drug-related AE or laboratory abnormality (including but not limited to creatinine, AST, ALT, or Total Bilirubin), except for the following events which do not require discontinuation:
  - Grade 4 neutropenia  $\leq 7$  days
  - Grade 4 lymphopenia or leukopenia or asymptomatic amylase or lipase

- Isolated Grade 4 electrolyte imbalances/abnormalities that are not associated with clinical sequelae and are corrected with supplementation/appropriate management within 3 calendar days of their onset
- Grade 4 drug-related endocrinopathy AEs, such as, hyper- or hypothyroidism, or glucose intolerance, which resolve or are adequately controlled with physiologic hormone replacement (corticosteroids, thyroid hormones) or glucose-controlling agents, respectively, may not require discontinuation after discussion with and approval from the BMS Medical Monitor/designee.
- Any AE, laboratory abnormality, or intercurrent illness which, in the judgment of the investigator, presents a substantial clinical risk to the participant with continued BMS-986205 and nivolumab dosing
- Any event that leads to delay in dosing of nivolumab lasting > 10 weeks from the previous dose requires discontinuation, with the following exceptions:
  - Dosing delays to allow for prolonged steroid tapers to manage drug-related AEs are allowed.
  - Dosing delays lasting > 10 weeks from the previous dose that occur for non-drug-related reasons may be allowed if approved by the BMS Medical Monitor/designee.
- Any event requiring 10 mg per day or greater prednisone or equivalent for more than 12 weeks except for adrenal replacement steroid dose >10mg

Prior to re-initiating treatment in a participant with a dosing delay lasting > 10 weeks, the BMS Medical Monitor/designee must be consulted. Tumor assessments should continue as per protocol even if dosing is delayed. Periodic study visits to assess safety and laboratory studies should also continue every 4 weeks or more frequently if clinically indicated during such dosing delays.

[figure not shown]
Participants who are discontinued from nivolumab, must also discontinue BMS-986205.

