## 9 STUDY ASSESSMENTS AND PROCEDURES

- Study procedures and timing are summarized in the Schedule of Activities ([Section 2](#)).
- Protocol waivers or exemptions are not allowed.
- All immediate safety concerns must be discussed with the Sponsor immediately upon occurrence or awareness to determine if the participant should continue or discontinue treatment.
- Adherence to the study design requirements, including those specified in the Schedule of Activities, is essential and required for study conduct.
- All screening evaluations must be completed and reviewed to confirm that potential participants meet all eligibility criteria before randomization. The investigator will maintain a screening log to record details of all participants screened and to confirm eligibility or record reasons for screening failure, as applicable.
- Procedures conducted as part of the participant's routine clinical management (eg, blood count) and obtained before signing of informed consent may be utilized for screening or baseline purposes provided the procedure meets the protocol-defined criteria and has been performed within the timeframe defined in the Schedule of Activities.

Additional measures, including non-study required laboratory tests, should be performed as clinically indicated or to comply with local regulations. Laboratory toxicities (eg, suspected drug induced liver enzyme evaluations) will be monitored during the follow-up phase via on site/local labs until all study treatment-related toxicities resolve, return to baseline, or are deemed irreversible.

If a participant shows pulmonary-related signs (hypoxia, fever) or symptoms (eg. dyspnea, cough, and fever) consistent with possible pulmonary AEs, the participant should be immediately evaluated to rule out pulmonary toxicity, according to the suspected pulmonary toxicity management algorithm in the BMS-936558 (Nivolumab) IB. In addition, blood methemoglobin levels should be evaluated to rule out methemoglobinemia (see [Section 7.4.6](#)) and CBC measured to rule out anemia in participants with dyspnea.

Some of the assessments referred to in this section may not be captured as data in the eCRF. They are intended to be used as safety monitoring by the treating physician. Additional testing or assessments may be performed as clinically necessary or where required by institutional or local regulations.

This study will consist of three phases: screening, treatment, and follow-up.

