## **COMPLIANCE WITH THE PROTOCOL AND PROTOCOL REVISIONS**

The investigator should not implement any deviation or change to the protocol without prior review and documented approval/favorable opinion of an amendment from the IRB/IEC (and if applicable, also by local health authority) except where necessary to eliminate an immediate hazard(s) to study subjects.

If a deviation or change to a protocol is implemented to eliminate an immediate hazard(s) prior to obtaining relevant approval/favorable opinion(s) the deviation or change will be submitted, as soon as possible to:

- IRB/IEC for
- Regulatory Authority(ies), if applicable by local regulations (per national requirements)

Documentation of approval/favorable opinion signed by the chairperson or designee of the IRB(s)/IEC(s) and if applicable, also by local health authority must be sent to BMS.

If an amendment substantially alters the study design or increases the potential risk to the participant: (1) the consent form must be revised and submitted to the IRB(s)/IEC(s) for review and approval/favorable opinion; (2) the revised form must be used to obtain consent from subjects currently enrolled in the study if they are affected by the amendment; and (3) the new form must be used to obtain consent from new subjects prior to enrollment.

If the revision is done via an administrative letter, investigators must inform their IRB(s)/IEC(s).

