7.5.3 Adverse Events Leading to Discontinuation of Study Therapy

A list of adverse events leading to discontinuation of study therapy will be provided for all treated participants.

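### Steroid stopping rule in Protocol 8.1.1 triggers at 10 mg/day or more but exempts adrenal replacement only above 10 mg, so replacement at exactly 10 mg/day is caught and a higher dose is not

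*Protocol*

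**What the plan says.** Protocol Section 8.1.1 lists the reasons for permanently stopping both BMS-986205 and nivolumab. Two bullets concern prolonged steroid use. One, early in the list, covers any "drug-related event requiring 10 mg per day or greater prednisone or equivalent for more than 12 weeks, except for adrenal replacement steroid dose >10mg". The other, at the end of the list, drops the drug-related qualifier: "Any event requiring 10 mg per day or greater prednisone or equivalent for more than 12 weeks except for adrenal replacement steroid dose >10mg". Both use the same pair of thresholds.

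Section 8.1 gives the list its force. Its opening sentence says, with a capitalised obligation, that participants are to "discontinue investigational product (and non-investigational product at the discretion of the investigator) for any of the following reasons", and one of the reasons is "Additional protocol-specified reasons for discontinuation", with a pointer to Section 8.1.1. Section 9 adds: "Protocol waivers or exemptions are not allowed".

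Two further provisions bear on adrenal cases. Sections 7.4.4 and 8.1.1 both state, within text on drug-related endocrinopathies: "Adrenal insufficiency requires discontinuation regardless of control with hormone replacement". Section 8.1.1 also lets a Grade 4 drug-related endocrinopathy that is controlled on physiologic replacement, corticosteroids included, continue if the Medical Monitor agrees.

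**The concern.** An exception for adrenal replacement exists because replacement makes up for missing hormone and is not treatment of an immune toxicity. It should therefore cover at least every replacement dose that would otherwise meet the trigger. Here it does not. The trigger is closed at 10 mg (10 and above) and the exception is open at 10 mg (above 10 only), which leaves one uncovered point. At that point the rule runs backwards: the lower replacement dose is stopped and the higher one is spared.

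At stake is treatment, not analysis. A literal application would permanently end nivolumab, and BMS-986205 for an Arm A participant still taking it, for a reason that is neither toxicity nor progression. The rule is still live. Enrollment closed on 19-Apr-2018 and treatment may run 104 weeks (about two years), so a participant randomized at closure could be treated until about April 2020, roughly 18 months after Revised Protocol 02 of 25-Oct-2018.

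**Working it through.** The plan gives no figure to reproduce. The check is one of logic.

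**Inputs** (Protocol 8.1.1): trigger, dose ≥ 10 mg/day prednisone equivalent for > 12 weeks; exception, adrenal replacement at > 10 mg.

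**Rule as written:** stop = (dose ≥ 10 and weeks > 12) and not (adrenal replacement and dose > 10).

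**Rule with the limit removed:** stop = (dose ≥ 10 and weeks > 12) and not (adrenal replacement).

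Evaluated at 13 weeks:

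| Dose (mg/day) | Adrenal, as written | Adrenal, limit removed | Other steroid use, as written | Other steroid use, limit removed |
|---|---|---|---|---|
| 5, 7.5, 9.9 | continue | continue | continue | continue |
| **10** | **stop** | **continue** | stop | stop |
| 10.1, 12.5, 15, 20 | continue | continue | stop | stop |

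Of the eight doses, 10 mg is the only one at which adrenal replacement forces a stop, and the only one at which the change alters an outcome. Moving the exception to ≥ 10 mg would give the same table, because below 10 mg the trigger is never met.

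**Which adrenal cases reach this point?**

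- *Drug-related adrenal insufficiency.* It generally stops under the separate adrenal-insufficiency sentence, whatever the replacement dose. The Grade 4 allowance in 8.1.1 is not reconciled with that sentence, so a drug-related case allowed to continue on corticosteroid replacement cannot be ruled out. Such a case at exactly 10 mg/day would meet both steroid bullets.
- *Not drug-related, new or worsened on study.* The final bullet has no drug-related qualifier, so it applies. This is the clear case.
- *Stable replacement already in place at entry.* The bullet requires an event. Appendix 3 defines an adverse event as something new, or a worsening of an existing condition. Unchanged replacement is arguably neither.

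**Comparison with entry.** Exclusion criterion 1(e) in Section 6.2 sets the general steroid limit at > 10 mg and permits adrenal replacement at > 10 mg. Both sides use the same inequality, so no gap arises there. In 8.1.1 the same > 10 mg phrase stands beside a ≥ 10 mg trigger.

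**Do the two bullets conflict?** Take dose (below, at, above 10 mg) by reason (adrenal, other) by drug-related (yes, no): 3 × 2 × 2 = 12 combinations. The any-event bullet stops 6 and the drug-related bullet stops 3, all of them among those 6. The second is redundant, not contradictory.

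**The case against.** The strongest reply is that this is a boundary slip whose intent nobody would mistake. The wording looks carried over from the entry criterion, 8.1.1 itself says treatment *should* be discontinued, and a sensible site would not stop a participant on physiologic replacement. That the intent is obvious stands, and it is why this is a drafting error and not a criticism of a design decision. The softer verb helps little, because Section 8.1 turns the 8.1.1 reasons into an obligation and Section 9 rules out waivers. Where the sponsor wanted discretion it wrote it in (Grade 3 AST or ALT, Grade 4 endocrinopathy, long delays for non-drug-related reasons); the steroid bullets carry none.

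Three limits also stand. The rule needs an event, so a reader might infer that anyone who entered on 10 mg/day replacement must be withdrawn after 12 weeks; the text does not clearly say so. A reader might also infer that drug-related cases are wholly outside the problem; the Grade 4 allowance means only that they generally are. And Section 7.7, together with Appendix 14, is redacted, so a clarification given there cannot be excluded.

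Finally, that one row of the table changes says nothing about frequency. It is a single point on a continuous dose scale, and the documents do not show that any participant has met it.

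**Conclusion.** The threshold is wrong as written, and the error is minor. Taken literally, 8.1.1 requires a permanent stop when an on-study event judged not drug-related needs adrenal replacement at exactly 10 mg/day for more than 12 weeks, and exempts the same participant at any higher dose. Nothing in the visible text closes the gap.

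The conclusion rests on reading the two inequalities literally, on the list being mandatory through Section 8.1, and on no correction lying in the redacted text. The number of participants affected is not given and is probably very small.

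A reader might infer that the error distorts the trial's results. The documents do not support that. Efficacy analyses were dropped under Revised Protocol 01, and the safety analyses are descriptive. The most direct output is SAP 7.5.3, which says: "A list of adverse events leading to discontinuation of study therapy will be provided for all treated participants". That listing would still record correctly any adverse event that led to a stop.

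**What to change.** In both bullets of Section 8.1.1, delete the >10mg limit so that the exception covers adrenal replacement steroids at any dose. Keep the trigger of 10 mg/day or more, for more than 12 weeks, for all other steroid use. Merging the two bullets is optional tidying and changes no instruction.

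The cost is one wording edit, with no new data, visits or procedures. Because it changes who must stop treatment, the cautious route is the next protocol revision: Appendix 2 says the investigator "should not implement any deviation or change to the protocol without prior review and documented approval/favorable opinion of an amendment" by the IRB/IEC. The sponsor has used administrative letters for typographical and contraceptive-wording clarifications, and Appendix 2 recognises that route, with notice to the IRB/IEC. It is a possible alternative if the sponsor regards this as correcting a slip. The stop for non-adrenal steroid use stays exactly as it is.

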### **8.1.2 BMS-986205 Dose Discontinuation**

The following events require discontinuation of BMS-986205 only; nivolumab may continue to be administered unless other events occur that would require delay or discontinuation of nivolumab as described in [Sections 7.4.3](#) and [8.1.1](#).

- Any event requiring more than 1 dose reduction of BMS-986205
- Any AE, laboratory abnormality, or intercurrent illness which, in the judgment of the investigator, presents a substantial clinical risk to the participant with continued BMS-986205 dosing
- For participants who delay BMS-986205 but continue nivolumab (see [Section 7.4.3](#)), any dose delay of BMS-986205 lasting > 10 weeks will result in the discontinuation of both BMS-986205 only.
- Per Revised Protocol 01, participants are permitted to discontinue BMS-986205, and continue nivolumab at investigator discretion (see [Section 3.1.1](#))
- Any occurrence of serotonin syndrome

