### **9.2.7 Laboratory Test Result Abnormalities**

The following laboratory test result abnormalities should be captured on the non-serious AE CRF page or SAE Report Form electronic, as appropriate. Paper forms are only intended as a back-up option when the electronic system is not functioning.

- Any laboratory test result that is clinically significant or meets the definition of an SAE
- Any laboratory test result abnormality that required the participant to have study treatment discontinued or delayed/ interrupted
- Any laboratory test result abnormality that required the participant to receive specific corrective therapy

It is expected that wherever possible, the clinical rather than laboratory term would be used by the reporting investigator (eg, anemia versus low hemoglobin value).

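### Protocol Sections 8.1.1 and 8.1.2 disagree on whether nivolumab stops after serotonin syndrome, and after a second BMS-986205 dose reduction unrelated to methemoglobinemia or QTc prolongation

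*Protocol*

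**What the plan says.** Section 8.1.1 of the protocol opens with "BMS-986205 and nivolumab treatment should be permanently discontinued for the following". Its first bullet is "Any occurrence of serotonin syndrome". A later bullet covers events that need more than one BMS-986205 dose reduction, "except for those related to methemoglobinemia or QTc prolongations, which require only discontinuation of BMS-986205 alone". It states that nivolumab may go on in those two situations and refers the reader to Section 8.1.2.

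Section 8.1.2 opens with "The following events require discontinuation of BMS-986205 only; nivolumab may continue to be administered unless other events occur" and refers to Sections 7.4.3 and 8.1.1 for those other events. Its first bullet is "Any event requiring more than 1 dose reduction of BMS-986205", with no limit on cause. Its last bullet is serotonin syndrome, worded exactly as in Section 8.1.1.

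Two other sections bear on the point:

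- Section 7.4.2 allows one reduction, from 100 mg to 50 mg. If another is needed, the participant must stop study treatments (plural), with a pointer to Section 8.1.1. It does not repeat the methemoglobinemia and QTc exception.
- Section 8.1 has the two drugs assessed separately. Nivolumab may continue when the criteria are met for BMS-986205 but not for nivolumab.

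**The concern.** These are stopping rules for Arm A participants who still take BMS-986205. A site that turns to Section 8.1.2 can keep giving nivolumab where Section 8.1.1 requires a permanent stop. A site that turns to Section 8.1.1 will end nivolumab where Section 8.1.2 allows it. The same event can then be handled in opposite ways, and either site can point to protocol text. Section 9 allows no waivers, so a site that follows one list is at odds with the other.

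Safety is the only analysis left in this trial. SAP Sections 7.5.2 and 7.5.4 summarise serious and other adverse events within 30 days of the last dose of study treatment. Nivolumab is study treatment under protocol Section 7, so the decision to stop or continue it moves the end of that window.

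**Working it through.** No arithmetic underlies the conflict itself. The check is to take each trigger and read both sections.

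| Event | Section 8.1.1 | Section 8.1.2 | Result |
|---|---|---|---|
| Serotonin syndrome, any occurrence | Stop both | Stop BMS-986205 only | Conflict |
| Second reduction, methemoglobinemia or QTc | Stop BMS-986205 only | Stop BMS-986205 only | Agree |
| Second reduction, any other cause | Stop both | Stop BMS-986205 only | Conflict |

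Section 8.1.2 has five bullets: more than one reduction, investigator-judged risk, a BMS-986205 delay beyond 10 weeks, investigator discretion under Revised Protocol 01, and serotonin syndrome. The first and the last conflict with Section 8.1.1, which is 2 of 5. For the second-reduction case, Section 7.4.2 makes a third variant: it stops both drugs but omits the exception.

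**Does the proviso in Section 8.1.2 settle it?** No. It ends nivolumab only if *other* events occur, and the two triggers are themselves on the Section 8.1.2 list. If Section 8.1.1 always prevailed, the serotonin bullet in Section 8.1.2 would do nothing.

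**How wide is the second conflict?** Section 7.4.2 names Grade 3 fatigue, nausea, vomiting and anemia as reduction triggers besides methemoglobin and QTcF. Section 8.1.1 separately stops both drugs for "Any Grade 3 non-skin, drug-related AE lasting > 7 days, or recurs", subject to listed exceptions. That removes many cases. What remains is mainly:

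- a second Grade 3 trigger that differs from the first, or is short-lived;
- anemia, if it is handled as a laboratory abnormality, since "Grade 3 drug-related laboratory abnormalities do not require treatment discontinuation except" is followed only by thrombocytopenia and liver-test exceptions. Section 9.2.7 prefers clinical terms and uses anemia as its example, but nothing says how anemia is classed for Section 8.1.1;
- lower-grade events for which the dose was reduced on clinical judgment, in consultation with the Medical Monitor (Section 7.4.2).

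**Were the rules still in use?** Enrollment closed on 19-Apr-2018. The first dose was due within 3 calendar days of randomization (Table 2-2), and treatment may run 104 weeks from the first nivolumab dose (Synopsis, Duration). For a participant randomized on the closing day, the latest first dose is 22-Apr-2018. Adding 104 × 7 = 728 days gives 19-Apr-2020. Revised Protocol 02 is dated 25-Oct-2018, so its rules could apply for just under 18 months.

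**The case against.** The best counter-argument is that other text narrows both conflicts, and much of that is right.

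- Section 8.1 stops both drugs when the investigator cannot tell which one caused the event. An investigator who attributes it to BMS-986205 alone is outside that rule.
- Section 9 requires immediate safety concerns to be discussed with the sponsor to decide on continuation. Serotonin syndrome would plausibly qualify, which makes it less likely that sites diverge unnoticed. The sponsor would still be reading two contrary lists.
- Section 7.4.3 delays both drugs for Grade 3 drug-related fatigue, nausea, vomiting and anemia, and for most Grade 2 non-skin drug-related events. For those events the choice is between holding and later resuming nivolumab and ending it permanently. It is not between ending it and uninterrupted dosing.
- Drug-related serotonin syndrome at Grade 4, or at Grade 3 lasting more than 7 days or recurring, meets separate Section 8.1.1 criteria for stopping both drugs. The practical gap is milder or brief, non-recurrent episodes.
- On the second reduction, Sections 8.1, 8.1.1 and 7.4.2 read together favour stopping both drugs. The Section 8.1.1 reference to Section 8.1.2 suggests that bullet was meant for methemoglobinemia and QTc events only.
- If nivolumab continues, a longer adverse event window is that window working as defined, and no bias has been shown.

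These points reduce how often the conflict matters. None removes the double listing or supplies the missing limit in Section 8.1.2.

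It is also fair to say that the public text does not show which serotonin rule the sponsor intended. Appendix 16 records that Revised Protocol 01 updated both sections. Section 7.7.2, where it added serotonin precautions, is redacted. The correction should therefore leave room for the sponsor's answer.

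**Conclusion.** The concern holds. The serotonin syndrome conflict is direct. The second-reduction conflict is real but narrow, and the weight of the text supports Section 8.1.1. This should be fixed.

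Its size cannot be given in participants or events, because the documents report neither the incidence of these events nor how many participants remain on BMS-986205. The exposed group is confined to Arm A and is reduced further by the option, under Revised Protocol 01, to drop BMS-986205 and continue nivolumab. The consequences are for safety management and consistent conduct. The effect on the safety tables is a possible shift in which events fall within 30 days of the last dose; its direction and amount are unknown. No efficacy result is affected, since none is planned.

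The conclusion rests on the visible text. Section 7.7.2 may clarify intent on serotonin syndrome, but it would not undo the contradictory lists.

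**What to change.** 1. **Serotonin syndrome:** keep it in one section. The default is to delete the last bullet of Section 8.1.2, so that Section 8.1.1 governs. This is the more protective rule; the trade-off is that it permanently ends nivolumab for anyone who has the event. If the sponsor checks Section 7.7.2 and documents that nivolumab may continue, delete the bullet from Section 8.1.1 instead.
2. **Section 8.1.2, first bullet:** after the word *event*, insert *related to methemoglobinemia or QTc prolongation*.
3. **Section 7.4.2, last sentence:** add *except for events related to methemoglobinemia or QTc prolongation, where only BMS-986205 is discontinued (see Sections 8.1.1 and 8.1.2)*.
4. **Clerical:** in the Section 8.1.2 bullet on delays beyond 10 weeks, delete the stray word *both*.

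The cost is one deleted bullet, two edited sentences and one deleted word, in an amendment or administrative letter with ethics committee review or notice as applicable. It needs no new data, visits or participants.
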